### 7.3 Adverse Events and Serious Adverse Events

An adverse event is any unintended medical occurrence (symptom, diagnosis, sign, abnormal laboratory finding, or missed study procedure) that occurs during the study that was not present at baseline.

- Any medical condition present at the time of enrollment is considered baseline, and not reported as an adverse event.
- If the severity of a pre-existing medical condition worsens at any time during the study participation, it will be considered an adverse event.
- All adverse events will be assessed by the Principal Investigator to determine the severity of the event (mild, moderate, severe, life-threatening) and whether the event is related to the study product or study intervention
- All AEs will be recorded in the eCRF in the study database. The event description, date of onset and study clinician's assessment of severity and relationship to study product, date of resolution and outcome will be recorded. To elicit any adverse event, the parent will be prompted at each encounter to report any change in their child since the last contact.

A serious adverse event (SAE) is any unintended medical occurrence in which the patient outcome is death or life-threatening hospitalization, disability, or incapacity.

- In the event of an SAE, the SAE eCRF must be completed by the research coordinator and the details of the relevant SAE should be notified to the PI ([name]) immediately. The event description, date of onset and study clinician's assessment of severity and relationship to study product, and outcome of event will be recorded.
- SAEs will be logged in the electronic database and will be periodically monitored by the study statistician.

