### 7.4 Reporting Procedures

- All AEs will be reported to the Data and Safety Monitoring Board annually.
- Unanticipated protocol-related problems will be notified by the PI ([name]) to the IRB as and when they occur
- All SAEs must be reported by the research staff to [name], the study principal investigator, immediately. Principal investigator will report SAEs to the University of Pittsburgh Institutional Review Board (IRB) according to the local IRB requirements. SAEs related to the research intervention will be notified by the PI ([name]) to the IRB within 24 hrs. AEs of moderate severity related to the research intervention will be notified by the PI ([name]) to the IRB within 5 days.

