## 7.6 Safety Monitoring

- Members of the Data and Safety Monitoring Board will evaluate participants' risks (adverse events) vs. the benefits and other factors that can affect study outcome.
- Real-time reports of SAEs will be sent to the Data and Safety Monitoring Board as determined by the principal investigator.
- We will appoint an Independent Safety Monitor (ISM) who will have expertise in pediatrics and whose primary responsibility will be to provide timely safety monitoring, to ensure good clinical practice and to quickly identify safety concerns. Safety reports by the ISM will be submitted on a regular basis, (e.g., real time, weekly, monthly, quarterly) as determined by the DSMB. To minimize bias, the ISM will evaluate SAEs masked to treatment assignment, unless the DSMB approves partial or complete unmasking. The ISM will participate for the duration of the study.
- The ISM will be able to readily access participant records. The primary focus of the ISM is to independently review SAEs that may be associated with study treatment as well as adverse events of special interest. The ISM will investigate any events considered serious and unexpected. The ISM will be in communication with [name] and the DSMB chair for any event that needs further evaluation. The ISM will not be directly involved in the trial, will not be under the investigator's supervision, and will have no financial, intellectual, proprietary or professional interest in the outcome of the trial.

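### The only SAE definition runs life-threatening and hospitalization together, so some admissions and some life-threatening events can miss the SAE pathway

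*Combined protocol and SAP*

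**What the plan says.** Section 7.3 defines the term once. An SAE is an occurrence "in which the patient outcome is death or life-threatening hospitalization, disability, or incapacity". No other section gives a second definition or a list of criteria.

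The same section has the PI assess every adverse event "to determine the severity of the event (mild, moderate, severe, life-threatening"), with no statement of how that grade relates to seriousness.

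Reporting then depends on SAE status:

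- **Section 7.3:** the coordinator completes an SAE form and tells the PI at once.
- **Section 7.4, SAEs:** "All SAEs must be reported by the research staff to" the PI immediately. Those related to the intervention go "to the IRB within 24 hrs"; the rest follow local IRB requirements.
- **Section 7.4, other events:** related events of moderate severity go to the IRB within 5 days, and unanticipated protocol-related problems go as they arise. For the board, "All AEs will be reported to the Data and Safety Monitoring Board annually".
- **Section 7.5:** follow-up rules for non-serious events graded mild, moderate or severe.
- **Section 7.6:** real-time SAE reports to the DSMB at the PI's determination. For the Independent Safety Monitor (ISM), "The primary focus of the ISM is to independently review SAEs that may be associated with study treatment", together with adverse events of special interest, a term the protocol does not define.
- **Section 9.2, Treatment Assignment Procedures:** an SAE may lead to unmasking.
- **Sections 9.3 and 10.3 (Metrics):** SAEs are listed individually and tabulated as rates overall and by arm.

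**The concern.** An SAE definition normally names a life-threatening event and a hospitalization as separate criteria. Here the adjective stands directly before the noun, with no comma or conjunction, so the two become one narrower criterion. The coordinator has to decide from this sentence whether to open an SAE form. One coordinator may apply it literally and another may read it as a list, so similar events could be classified differently.

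At stake are how quickly certain events are seen outside the study team and whether the SAE tables by arm mean the same thing throughout. This is a comparison of three doses in children aged 10 to 18, and the DSMB's closed-session comparison of SAE rates is only as consistent as the definition behind it.

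**Working it through.** No arithmetic applies and the plan states no figure to reproduce. The check reads the definition two ways and follows each kind of event through the sections that depend on SAE status.

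**Step 1: classify.** The literal reading takes the words as printed. The list reading supposes a missing separator after life-threatening. In rows 1 to 3 the event does not end in death, disability or incapacity.

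| Event | SAE, literal reading | SAE, list reading |
|---|---|---|
| 1. Admission that is life-threatening | Yes | Yes |
| 2. Admission that is not life-threatening | No | Yes |
| 3. Life-threatening event, no admission | No | Yes |
| 4. Any event ending in death, disability or incapacity | Yes | Yes |

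The readings differ only in rows 2 and 3.

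**Step 2: what rows 2 and 3 miss on the literal reading.** They miss the SAE form and immediate PI notice (7.3, 7.4), the SAE route to the IRB including the 24-hour limit if related (7.4), real-time DSMB reports where the PI calls for them and ISM review of SAEs (7.6), the unmasking provision (9.2), and the SAE listings and rates by arm (9.3, 10.3).

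**Step 3: what still reaches them.**

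- *Both rows:* entry in the adverse event form with description, onset, severity, relatedness and outcome (7.3); the annual report to the DSMB (7.4); the IRB as an unanticipated protocol-related problem, if the event is one (7.4); the ISM, if it counts as an event of special interest (7.6).
- *Row 2, graded moderate and related:* the IRB within 5 days (7.4).
- *Row 2, graded severe and related:* the 5-day rule does not name it. Section 7.5 gives it follow-up but sets no reporting deadline.
- *Row 3, graded life-threatening and related:* the 5-day rule does not name it, and section 7.5 has no rule for that grade.

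**Step 4: compare deadlines.** For related events, the text gives an SAE 24 hours to the IRB and a moderate non-serious event 5 days. A life-threatening event classed as non-serious has no stated deadline, unless it is also an unanticipated protocol-related problem. The grade above moderate and severe is thus treated less urgently than moderate, an ordering the authors are unlikely to have intended.

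**The case against.** The strongest reply is that this is a dropped separator and everyone will read it as a list. Section 7.3 has four severity grades, and section 7.5 gives non-serious follow-up rules for all but the life-threatening grade. That suggests the authors took life-threatening events to be serious in every case. A comma may even have been lost when the PDF was converted, though nothing shows this. The inference about intent is fair. It does not remove the point: the available text never says that the life-threatening grade implies seriousness, and section 7.5 is silent on hospitalization. If a list was meant, printing it as a list does no harm.

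The reply also limits the consequences, and those limits stand. A reader might infer any of the following, and the documents do not support them:

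- *That these events escape expedited review altogether.* They can miss the SAE pathway, but the other IRB routes in 7.4 and the special-interest route in 7.6 remain. The ISM can also readily see participant records, and the Monitoring text after section 10.3 puts adverse-event data under ongoing monitoring.
- *That a life-threatening event is serious only if it leads to admission.* Death, disability and incapacity also qualify.
- *That every such event reaches the DSMB up to 12 months late instead of in real time.* Twelve months is the longest interval under the annual report. Real-time reports are at the PI's determination even for SAEs, and the DSMB may set a shorter interval for ISM reports.
- *That serious harms will be undercounted.* All adverse events are recorded with enough detail to reclassify them. The risk is inconsistent classification in the SAE tables, not loss of events.

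Serum calcium, the main laboratory safety parameter, has its own pathway in sections 7.1, 7.2 and 8, independent of SAE status.

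**Conclusion.** The point holds in limited form. As worded, the only SAE definition leaves out two kinds of event unless they end in death, disability or incapacity: a hospitalization that is not life-threatening, and a life-threatening event without admission. These can miss the SAE pathway while still being recorded and reported to the DSMB at least annually. The firmest part is the gap between sections 7.3, 7.4 and 7.5: a related life-threatening event classed as non-serious has neither a stated IRB deadline under the 5-day rule nor a follow-up rule.

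The size cannot be given as a number, because the documents contain no expected rate of admissions or life-threatening events. Participants are otherwise healthy, so such events may be few, but that is an assumption. The conclusion rests on the printed wording and on there being no second definition in the available text. It concerns safety reporting only; the primary outcome, sample size, power and alpha are unaffected. It should be corrected.

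**What to change.** In section 7.3, replace the sentence with separate criteria: death; life-threatening event; hospitalization; disability; incapacity. Add that any event graded life-threatening is serious. Then reconcile sections 7.4, 7.5 and 7.6 with that list, so that every combination of severity and relatedness has a stated reporting route.

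If the joint wording is intended, say so and state the reporting route for the events it leaves out.

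If the change is made after enrolment has begun, review the adverse events already recorded against the new list and reclassify where needed, masked to arm, so that the SAE tables use one definition throughout.

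The cost is a short amendment, a few more SAE forms and, where it applies, one pass through the existing adverse event records.

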### 7.4 Reporting Procedures

- All AEs will be reported to the Data and Safety Monitoring Board annually.
- Unanticipated protocol-related problems will be notified by the PI ([name]) to the IRB as and when they occur
- All SAEs must be reported by the research staff to [name], the study principal investigator, immediately. Principal investigator will report SAEs to the University of Pittsburgh Institutional Review Board (IRB) according to the local IRB requirements. SAEs related to the research intervention will be notified by the PI ([name]) to the IRB within 24 hrs. AEs of moderate severity related to the research intervention will be notified by the PI ([name]) to the IRB within 5 days.

### 7.5 Follow-up for Adverse Events

- Follow-up of a non-serious adverse event of mild or moderate severity will end when the study reporting period ends [i.e., 6-month follow-up visit (final study visit)]. Study staff will keep apprised of subject's adverse event until the parent/subject provides a date of resolution for the AE; resolution date will be documented in the CRHC database.

- Follow-up for a non-serious adverse event of severe nature will be the following:
  - At the time of the event, the investigator will provide appropriate treatment or follow up, including communicating the event to the child's primary care provider and/or providing a referral to a specialist.
  - The staff will place a follow up phone call to the parent, regardless of the study reporting period, to assure that the child is improving or that the family has connected with the suggested referral. Study staff will keep apprised of subject's adverse event until the parent/subject provides a date of resolution for the AE; resolution date will be documented in the CRHC database.

## 7.6 Safety Monitoring

- Members of the Data and Safety Monitoring Board will evaluate participants' risks (adverse events) vs. the benefits and other factors that can affect study outcome.
- Real-time reports of SAEs will be sent to the Data and Safety Monitoring Board as determined by the principal investigator.
- We will appoint an Independent Safety Monitor (ISM) who will have expertise in pediatrics and whose primary responsibility will be to provide timely safety monitoring, to ensure good clinical practice and to quickly identify safety concerns. Safety reports by the ISM will be submitted on a regular basis, (e.g., real time, weekly, monthly, quarterly) as determined by the DSMB. To minimize bias, the ISM will evaluate SAEs masked to treatment assignment, unless the DSMB approves partial or complete unmasking. The ISM will participate for the duration of the study.
- The ISM will be able to readily access participant records. The primary focus of the ISM is to independently review SAEs that may be associated with study treatment as well as adverse events of special interest. The ISM will investigate any events considered serious and unexpected. The ISM will be in communication with [name] and the DSMB chair for any event that needs further evaluation. The ISM will not be directly involved in the trial, will not be under the investigator's supervision, and will have no financial, intellectual, proprietary or professional interest in the outcome of the trial.

## 8. INTERVENTION DISCONTINUATION

To ensure children's safety, we will use a serum calcium cutoff of >10.8 mg/dL in 10- to 14-year-old children and >10.2 mg/dL in  $\geq$ 15-year-old children to prompt further evaluation. An elevated serum calcium level will be repeated and if it remains abnormal, study medication will be discontinued, and participant will be withdrawn from the study protocol. Children who discontinued study medication due to hypercalcemia will have serum 25(OH)D measured to rule out vitamin D toxicity (levels  $\geq$ 100 ng/mL) and will be evaluated by a pediatric endocrinologist. Children with hypercalcemia and normal serum 25(OH)D levels (<100 ng/mL) will be referred for further evaluation to their primary care provider and a pediatric endocrinologist to rule out other unusual causes of hypercalcemia (chronic granulomatous disorders, primary hyperparathyroidism, familial hypocalciuric hypercalcemia).

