### Prohibited Interventions

Participants are expected to not take the following medications during their participation in the study. If these medications are clinically necessary and prescribed by a provider, the participant may be withdrawn from the study based on the PI's discretion.

- Multivitamins
- Anticonvulsants
- Systemic glucocorticoids
- Antipsychotics
- Antihypertensives
- Vasoactive drugs
- Antilipidemics
- Metformin or other oral insulin regulators
- Chemotherapeutics or other cancer treatments

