## **7. SAFETY ASSESSMENTS**

### **7.1 Specification of Safety Parameter**

- Serum calcium levels will be monitored for participant safety. Serum calcium  $>10.8$  mg/dL in 10- to 14-year-old children and  $>10.2$  mg/dL in  $\geq 15$ -year-old children will prompt further evaluation. An elevated serum calcium level will be repeated and if still abnormal, study medication will be discontinued. Children who discontinued study medication due to hypercalcemia will have serum 25(OH)D measured to rule out vitamin D toxicity (levels  $\geq 100$  ng/mL) and will be referred to a pediatric endocrinologist for further evaluation and management. Children with hypercalcemia and normal serum 25(OH)D levels ( $<100$  ng/mL) will be also be referred for further evaluation to their primary care provider and a pediatric endocrinologist to rule out other unusual causes of hypercalcemia (chronic granulomatous disorders, primary hyperparathyroidism, familial hypocalciuric hypercalcemia).
- Significant fasting hyperglycemia (fasting blood glucose  $>125$  mg/dL) during enrollment visit will disqualify subject from enrolling in the study.
- Post-menarchial girls that test positive during pregnancy screen at the enrollment visit will be excluded. Positive screens in the final visit will disqualify subject from getting a DXA scan but will not exclude subject from completing the study.
- At the 3-month follow-up and the final visit, the MEMS cap data will be downloaded to assess adherence.

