### **7.2 Methods and Timing for Assessing, Recording, and Analyzing Safety Parameters**

Serum calcium will be measured at the screening visit and only children with normal calcium results for age will be eligible to enter the study. Upon enrollment, serum calcium will be monitored for safety at the 3-month and 6-month follow-up visits, and children found to have elevated serum calcium ( $>10.8$  mg/dL in 10- to 14-year-old children and  $>10.2$  mg/dL in  $\geq 15$ -year-old children) will be further managed as stated above in section 7.1.

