## 9.5 Data Analyses

Our primary analysis will use children's original treatment assignment regardless of adherence (intention to treat). We will begin by calculating descriptive statistics for baseline demographics and clinical characteristics by vitamin D treatment groups (600 IU vs 1000 IU vs 2000 IU). Our primary outcome measure of vascular health is brachial artery FMD expressed as a percentage. We will use mixed-effects models with fixed effects of time (baseline, 3 months, and 6 months), the treatment\*time interaction, and random subject effects to test for differential changes in FMD over time and differences in FMD at six months. We are primarily interested in the comparisons of each higher dose (1000 IU and 2000 IU) to the lower dose (600 IU) at six months ( $\alpha=0.025$  for each comparisons). The mixed-effects model will allow unbiased estimation of the treatment effects at six months even if some 6-month data are missing because of the incorporated dependence among baseline, 3-month and 6-month assessments (assuming data are missing at random). We will test the main effect of vitamin D supplementation (three groups) at 3 and 6 months and pairwise comparisons of the groups receiving the larger doses of vitamin D with the group receiving 600 IU. If differences are detected across the 3 groups, we will test for a dose response in FMD across doses by using a linear contrast of coefficients test ( $\alpha=0.05$ ). We will use the same methodology to test the effects of higher doses of vitamin D on pulse-wave velocity, our primary measure of arterial stiffness.

The second part of our primary analysis of our trial is to determine whether higher doses of vitamin D will result in improvements in insulin sensitivity and metabolic syndrome markers over time. We will use mixed-effects models with fixed effects of time (baseline, 3 months, and 6 months), and the treatment time interaction with random subject effects to test for differential changes in secondary outcomes over time. We will test the main effect of treatment (three groups) at 3 and 6 months and pairwise comparisons of the groups receiving the larger doses of vitamin D with the group receiving 600 IU. All tests will be two sided with  $\alpha=0.05$ .

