### Missing Data

We do not expect substantial missing item-response data due to the electronic nature of data collection. Based on our pilot work, we anticipate <20% attrition at the 6-month assessment, and we have accounted for this in sample-size analyses. Participants who wish to discontinue the study drug will be asked to continue to participate in all follow-up visits; those who no longer wish to participate in the study will be considered dropouts, and we will monitor these events. We will obtain reasons for dropout in case it appears possible to modify the protocol so as to increase retention. At the end of the study, we will compare baseline characteristics and treatment arms between participants who have received 3- and 6-month assessments and participants who have not, to learn what factors are associated with missing visits.

For participants with missing 6-month outcome data, we will conduct several sensitivity analyses to test the impact on our study conclusions. The methods proposed assume that the data are missing at random (MAR), where the missing data mechanism is related to observed data, not the unobserved values. Although this assumption is difficult to confirm, our sensitivity analyses will allow us to assess the robustness of our findings and threats to the MAR assumption. Given that our outcomes are highly mechanistic and less patient-relevant symptomatic/functional outcomes, missing data at 6 months would likely be related to baseline characteristics or 3-month values. As mentioned previously, we will use linear mixed models for analysis, since these models are more robust to missing data than traditional multivariate models or single-point-in-time ANOVA. From these models, we can estimate the treatment impact at 6 months using the covariance structure of the repeated measurements. This approach will be compared to a complete case analysis (missing complete at random) and a nonignorable missing data method (pattern mixture modeling). These different methods should result in consistent qualitative results if our findings are robust to missing data.

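### Section 8 takes a child with confirmed high calcium out of the study protocol, section 7.1 only stops the tablets, and no text keeps that child's 6-month outcome visit

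*Combined protocol and SAP*

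**What the plan says.** Three places deal with confirmed high calcium.

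- Section 8 (Intervention Discontinuation): "study medication will be discontinued, and participant will be withdrawn from the study protocol".
- Section 7.1 (Specification of Safety Parameter): "An elevated serum calcium level will be repeated and if still abnormal, study medication will be discontinued". It then gives the 25(OH)D measurement and referral, and does not mention withdrawal.
- Section 7.2, for calcium found high at the 3- and 6-month visits: such children "will be further managed as stated above in section 7.1". It does not point to section 8.

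Retention is covered under Missing Data in section 9.5, which names two groups. For the first, "Participants who wish to discontinue the study drug will be asked to continue to participate in all follow-up visits". For the second, "those who no longer wish to participate in the study will be considered dropouts".

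The primary analysis in section 9.5 uses each child's "original treatment assignment regardless of adherence (intention to treat"). The primary outcome in section 9.4 is change in FMD% at 6 months. The Missing Data text also plans a complete-case analysis and a pattern-mixture analysis beside the mixed model.

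**The concern.** The same laboratory finding leads to different instructions depending on which section staff open. Under section 7.1 the child stops tablets and nothing is said to change in the visit schedule. Under section 8 the child also leaves the study protocol. That sentence has already stopped the tablets, so its second clause adds something only if it means leaving follow-up, and this is how staff are likely to read it.

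The retention sentence does not settle the matter. A child stopped by a safety rule has neither chosen to stop the drug nor declined to take part, and so falls in neither group.

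What is at stake is a 6-month measurement that could be taken at a visit already in the schedule. An intention-to-treat analysis wants that value whether or not the child is still on tablets. The trigger is also not neutral: calcium is the trial's named safety parameter in a comparison of three vitamin D doses, so these losses could plausibly differ by arm.

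**Working it through.** **Step 1. Who is exposed.** After enrollment, calcium is checked at 3 and 6 months (section 7.2). A high value at the final visit costs little, because the 6-month outcomes are measured at that same visit. The exposed child is one whose calcium is high at 3 months and is confirmed on repeat.

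**Step 2. Does other text keep the visit?**

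- Sections 7.3 and 7.5 treat an abnormal laboratory finding as an adverse event and follow it up. They do not provide for FMD, PWV or outcome bloods.
- The final-visit text in section 6.2 lets a girl with a positive pregnancy screen skip DXA and complete the rest. The protocol therefore already separates one unsuitable procedure from the whole visit.
- No section gives a safety reason why a child off tablets could not attend at 6 months.

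**Step 3. Reproduce the plan's power (section 9.2).** Inputs are 56 per arm, a difference of 1.6 points, SD 2.6, and two-sided alpha 0.025.

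- Noncentrality = 1.6 / (2.6 × √(2/56)) = 3.26. The t test gives 83.6% and the normal approximation 84.5%. The plan states 84%.
- Dropout: 56 / 0.75 = 74.7, so 75 per arm and 225 in total, as stated.

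**Step 4. Power if 6-month values are lost.** The documents give no rate of confirmed high calcium. Assumed rates of 0.5%, 1%, 2% and 5% of 229 give about 1, 2, 5 and 11 children across three arms. The table takes 1 to 3 lost per arm, on top of 25% dropout (t test).

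| Extra values lost | One arm only | Both arms compared |
|---|---|---|
| 0 | 83.6% | 83.6% |
| 1 | 83.2% | 82.8% |
| 2 | 82.8% | 82.1% |
| 3 | 82.4% | 81.3% |

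The 56 per arm is what remains after 25% dropout, so these losses may already be counted. With 229 enrolled and 20% attrition, the ceiling given under Missing Data, 229 / 3 × 0.80 = 61 remain per arm. Losing 3 more leaves 58 and 85.0% power, above the stated 84%. At the 30% upper end in section 9.2, 229 / 3 × 0.70 = 53 remain, which gives 81.3%, and that slack is gone.

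**Step 5. Worst-case bias.** Assume that k children are lost in one arm only, that they differ from the rest by d = 0.5 to 1 SD, and that the model recovers nothing. Bias = (k/56) × d × 2.6. Type I error comes from a noncentral t with 56 − k and 56 children.

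| k | Bias (points) | Share of 1.6 | Type I error (nominal 0.025) |
|---|---|---|---|
| 1 | 0.02–0.05 | 1–3% | 0.0252–0.0256 |
| 2 | 0.05–0.09 | 3–6% | 0.0256–0.0275 |
| 3 | 0.07–0.14 | 4–9% | 0.026–0.031 |

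**Step 6. What the mixed model recovers.** Take a random-intercept model with arm means free at each visit, and an assumed within-child correlation ρ of 0.3 to 0.7.

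- Difference already visible at 3 months: the model recovers ρ/(1+ρ), or 23–41%. Bias for k = 3 falls to 0.04–0.11 points.
- Difference visible at baseline and 3 months: it recovers 2ρ/(1+ρ), or 46–82%. Bias for k = 3 falls to 0.01–0.08 points.
- Difference arising only after 3 months: it recovers nothing.

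Equal loss in both arms, with the same difference, gives no between-arm bias.

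**The case against.** The strongest reply is that no lost visit is shown. Section 8 is headed as being about the intervention and cancels no visit, so its second clause could mean treatment only. Both sections stop the tablets, measure 25(OH)D and refer the child; section 8 adds one clause. Section 7.5 keeps staff in contact over the adverse event. The mixed model uses the baseline and 3-month values, and the plan already includes "a nonignorable missing data method (pattern mixture modeling"). The dropout allowance covers a few extra losses.

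Much of this stands. The clause is ambiguous, and the numerical effect is probably small. Two things remain. The narrow reading makes the clause redundant, so the text needs settling even if that reading was intended. And adverse-event contact and sensitivity analyses do not replace an outcome that could have been measured.

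A reader might infer more than the documents support:

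- **That intention to treat is breached.** It is not. Children are still analysed in the arm to which they were randomised.
- **That the FMD comparison is biased or power is lost.** The ranges above rest on assumed rates, one-sided loss and an assumed outcome difference. The documents give none of these.
- **That section 5.3 has the same fault.** There, a child who needs a listed drug "the participant may be withdrawn from the study based on the" investigator's discretion. This is permissive, no other section conflicts with it, and several listed drugs could themselves alter FMD, blood pressure, glucose or lipids. It is a trade-off, and it should be left alone.

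**Conclusion.** The point holds as a minor one. The difference between sections 8 and 7.1 is plain on the page, and so is the gap in the retention sentence. The consequence is conditional: a 6-month visit is lost only if high calcium is confirmed after the 3-month check and staff read section 8 as ending follow-up.

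The number of children is unknown and probably small. With up to three extra losses per arm on top of the full 25% dropout, power stays at or above 81.3%. The worst-case bias is 0.14 points against a 1.6-point target effect, under assumptions that the documents do not establish. The case for change is not that the result is at risk. It is that the rule could discard 6-month data because of a safety finding plausibly related to dose, and that this is easy to avoid.

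**What to change.** 1. In section 8, replace the clause that withdraws the child with an instruction to ask the child to attend all remaining study visits, where clinically appropriate. Stopping tablets, 25(OH)D testing and referral stay as they are.
2. Under Missing Data in section 9.5, extend the retention sentence to every child whose study tablets are stopped for any reason, unless consent or assent is withdrawn or a visit would be clinically unsafe.
3. Report the number of children whose tablets were stopped, by arm and reason.

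Section 5.3 needs no change.

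The cost is two short wording changes, one table row and a few visits that are already scheduled. Sample size and stated power do not change. The downside is that a few outcomes are measured off tablets, which an intention-to-treat analysis accepts.
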